## 4 Glossar

eBC	Early Breast Cancer
mBC	Metastatic Breast Cancer
ER $\alpha$	Estrogen-Receptor alpha
FDA	Food and Drug Administration
GCP	Good Clinical Practice
HER-2	Human Epidermal Growth Factor Receptor 2
HR	Hazard Ratio
IHC	Immunohistochemistry
NACT	Neoadjuvant chemotherapy
NGS	Next-Generation-Sequencing
OR	Odds Ratio
pCR	Pathological Complete Response
PR	Progesterone Receptor
SOP	Standard Operating Procedure
TCGA	The Cancer Genome Atlas
TNBC	Triple-Negative Breast Cancer
WES	Whole-Exome-Sequencing
WGS	Whole-Genome-Sequencing

## 5 Deutsche Kurzfassung

Studientitel	Molecular Mechanisms of Therapy resistant breast cancer (MOMENTUM) Molekulare Mechanismen von therapieresistentem Brustkrebs
Studienleiterin	[name]. [name]
Hintergrund	
Ungeachtet der therapeutischen Fortschritte haben Patientinnen mit Brustkrebs im Frühstadium (eBC), die nach einer neoadjuvanten Chemotherapie (NACT) keine pathologische Komplettremission (pCR) erreichen, immer noch ein höheres Rückfallrisiko. Insbesondere Patientinnen mit triple negativem Brustkrebs (TNBC) und/oder anderen biologischen oder klinischen Risikofaktoren haben eine schlechtere Prognose. In der fortgeschrittenen Erkrankungssituation erhalten Patientinnen in der Regel mehrere Behandlungslinien, um das Fortschreiten des Tumors zu verhindern. Bedingt durch Resistenzentwicklungen generieren spätere Therapielinien allgemein kürzer werdende Progressions-freie Überlebenszeiten als frühere Therapielinien. Einer der möglichen Gründe dafür ist die Tumorheterogenität.
 
Next generation sequencing (NGS) hat zu einem besseren Verständnis von Tumorheterogenität bei Brustkrebs geführt, welche mit Resistenzentwicklung und Überleben assoziiert ist. Mehrere Mutationen wurden identifiziert, die Drivermutationen für Tumorprogression sein könnten (Stephens Nature 2012, Koboldt Nature 2012, Curtis Nature 2012, Arnedos Nat. Rev. Clin. Oncol. 2015). Weitere Studien sind dringend erforderlich, um die Tumorheterogenität eingehend zu charakterisieren, insbesondere die molekularen Veränderungen, die unter/nach Einfluss von medikamentösem Selektionsdruck auftreten. Ein besseres Verständnis von Resistenzmechanismen ist notwendig, um neue Therapiestrategien und ggfs. potenzielle, neue Therapie Targets zu identifizieren.
 
MOMENTUM ist eine prospektive, nichtinterventionelle, translationale Registerstudie. Sie hat zum Ziel Patientinnen/Patienten mit eBC und relevanten, klinischem Residualtumor nach NACT sowie Patientinnen/Patienten mit metastasiertem Brustkrebs (mBC) und Progression unter/nach Systemtherapie über den zeitlichen Verlauf zu begleiten. Die registrierten Informationen aus dem klinischen Verlauf sollen mit Untersuchungen von longitudinalen Biomaterialien (Tumorgewebe/Blut) korreliert werden. Dabei sollen klinische Daten zu Therapien und Überleben unter dem Gesichtspunkt von Tumorheterogenität und Veränderungen von molekularen Biomarker Profilen über den zeitlichen Verlauf der Erkrankung systematisch analysiert werden.

Hypothese	Die Analyse von residualem Tumorgewebe nach NACT bei eBC sowie Tumorgewebe von Patientinnen/Patienten mit mBC und Progression unter/nach Systemtherapie ist relevant für die Identifizierung molekularer

	Mechanismen von Therapiesensitivität und Resistenzentwicklung sowie zur Identifizierung von neuen Therapie Targets.
Studienziele	
Studienziele
 
 
1. Untersuchen von Tumorheterogenität anhand der Analyse longitudinaler Tumorproben
 
2. Definieren von Biomarkern zur Vorhersage von Therapieresistenz in der neoadjuvanten, adjuvanten oder metastasierten Therapiesituation
 
3. Beschreiben von Veränderungen von Brustkrebssubtyp und Veränderungen molekularer Marker nach Systemtherapie
 
4. Identifizieren von neuen, prognostischen Biomarkern, die mit schlechterem Langzeitüberleben korrelieren (krankheitsfreies Überleben, progressionsfreies Überleben und Gesamtüberleben)
 
5. Identifizieren von neuen, prognostischen Biomarkern für Therapiesensibilität für post-neoadjuvante und palliative Systemtherapien
 
6. Identifizieren von neuen Therapie Targets, die für den Einsatz als post-neoadjuvante und palliative Systemtherapien untersucht werden können.
 

Studiendesign	
MOMENTUM ist eine prospektive, nichtinterventionelle, translationale Registerstudie. Die Registerstudie wird klinische Daten zu Patientinnen/Patienten mit eBC und residualem Tumor nach NACT, Patientinnen/Patienten mit Rückfall sowie Patientinnen/Patienten mit mBC erheben, bei denen mindestens zwei longitudinale Proben von Tumorgewebe (eine vor und eine nach Therapieeinfluss) verfügbar sind. Bei einer Studienteilnahme werden nur Gewebeproben gesammelt, die bei Maßnahmen der klinischen Routine gewonnen wurden (Diagnosestellung, Brustoperation, etc.) und daran Veränderungen der Tumorheterogenität und Entwicklung von Resistenzmechanismen im zeitlichen Verlauf untersucht. Zusätzlich werden Blutproben zum Zeitpunkt des Studieneintritts sowie bei Indikation zur Veränderung der Systemtherapie aufgrund von Progression gesammelt, um molekulare Mechanismen der Tumorprogression auf zirkulierender Tumor DNA (ctDNA)-Ebene zu überwachen (diese werden bei geplanten Blutabnahmen der klinischen Routine angeschlossen). Die Studie soll weitere Einblicke in die Tumorheterogenität von Brustkrebs zu entscheidenden Zeitpunkten der Erkrankung generieren und molekulare Mechanismen für Therapieresistenz analysieren.

Einschlusskriterien	
 
1. Patientinnen/Patienten mit eBC und relevantem klinischem Residualtumor nach NACT oder Fernrezidiv unter/nach (neo-)adjuvanter Therapie oder mit primär mBC und Progression nach mindestens einer Linie Systemtherapie
 
2. Alle Patientinnen/Patienten müssen ein Paar bestehend aus zwei longitudinalen Tumorgewebeproben zur Verfügung stellen können: 
 
• Eine Probe vor NACT und eine nach NACT für
 
 
 

	
Patientinnen/Patienten mit eBC
 
 
• Eine Probe vor und eine nach Krankheitsprogression für Patientinnen/Patienten mit mBC
 
 
3. Weibliche Patientinnen wie männliche Patienten <math>\geq 18</math> Jahre alt
 
4. Teilnahme ist unabhängig von histologischen Eigenschaften (duktale, lobuläre, andere Differenzierungen) und unabhängig vom Brustkrebssubtyp (luminal A, luminal B, HER2-positiv, TNBC) möglich
 
5. Unterschriebene Einverständniserklärung mit Einwilligung zur Sammlung klinischer Daten und Biomaterialien
 
6. Die Teilnahme an anderen, auch interventionellen Studien ist möglich.

Ausschlusskriterien	
1. Patientinnen/Patienten mit anderer maligner Vorerkrankung sind ausgeschlossen mit den folgenden Ausnahmen:
 
 
a. Erkrankungsfreiheit von mindestens 5 Jahren (letzte erkrankungsbezogene Untersuchung muss innerhalb von 3 Monaten vor Studieneinschluss erfolgt sein) und die die Primärerkrankung muss ein niedrig Risiko Profil aufweisen
 
b. Carcinoma in situ der Zervix Uteri, Basalzellkarzinom oder Plattenepithelkarzinom der Haut
 
 
2. Patientinnen/Patienten ohne histologische Sicherung der Brustkrebsdiagnose
 
3. Patientinnen/Patienten mit eBC oder primär mBC, die noch keine Systemtherapie für die Brustkrebserkrankung erhalten haben
 
4. Eine Entnahme von Gewebeproben durch Biopsie oder Operation nicht möglich
 
5. Jegliche physische oder psychische Beeinträchtigung oder schwerwiegende Komorbiditäten, die die eine adäquate Studienteilnahme nicht erlauben
 
6. Bekannte, signifikante, neurologische oder psychiatrische Erkrankungen, die das Verständnis der Studienziele und die informierte Einwilligung in die Studie nicht zulassen.

Studienmaßnahmen	
MOMENTUM ist eine nicht-interventionelle Registerstudie mit dem Fokus auf der Erfassung der Behandlung in der klinischen Routine und deren Korrelation mit molekularen Eigenschaften von Biopsien der klinischen Routine. Es werden nur Gewebeproben verwendet, die im Rahmen von Maßnahmen der Routine Versorgung (z.B. Biopsie bei Diagnosestellung, Operation, etc.) gewonnen wurden. Die Blutabnahmen für Vollblut- und Plasmaproben sollen zu Zeitpunkten von Blutabnahmen der Routine erfolgen. Es sind keine studienspezifischen Interventionen oder Untersuchungen vorgesehen. Der retrospektive Einschluss verstorbener Patienten mit sekundär mBC und Fernmetastasierung nach anfänglicher neoadjuvanter und/oder adjuvanter Therapie mit archivierten Biomaterialien und klinischen Daten ist in Einklang mit der "Empfehlung für die Bewertung forschungsbezogener Biobanken durch Ethik-Kommissionen empfohlen vom Arbeitskreis Medizinischer Ethik-

	Kommissionen Version 2.1. gemäß Beschluss vom 24.6.2022“ möglich.
Patientenanzahl	Circa 2000
Follow-up	Das Follow-up beträgt 5 Jahre
Zentren	Geplant circa 50 Studienzentren in Deutschland
Finanzierung	Die Finanzierung der Studie wird durch die GBG Forschungs GmbH sichergestellt

## 6 Synopsis

Study Title	Molecular Mechanisms of Therapy resistant breast cancer (MOMENTUM)
Coordinating Investigator	[name]. [name]
Study Background	
Despite recent therapeutic advances, early breast cancer (eBC) patients without pathologic complete response (pCR) after neoadjuvant chemotherapy (NACT) still have a high risk of relapse. Especially patients with triple-negative breast cancer (TNBC) and/or other biological or clinical high-risk features have a worse prognosis. In the advanced breast cancer setting, patients usually received multiple treatment lines to face tumor progression. However, each subsequent therapy line is less effective than earlier lines in prolonging patients' progression-free survival, and drug resistance develops. One of the reasons is the development of tumour heterogeneity.
 
Next generation sequencing has contributed significantly to the better understanding of the tumour heterogeneity of breast cancer, which is linked to treatment resistance and outcome. Several gene mutations were discovered as likely drivers of disease progression (Stephens Nature 2012, Koboldt Nature 2012, Curtis Nature 2012, Arnedos Nat. Rev. Clin. Oncol. 2015).
 
Further investigations are needed to deeply characterize breast cancer heterogeneity, in particular molecular alterations which occur during or after therapeutic pressure exerted through drug therapy. A better understanding of drug resistance mechanisms is crucial to the discovery of new potential treatment targets and the development of new therapeutic strategies with impact on survival outcomes.
 
MOMENTUM is a prospective registry trial with a non-interventional and translational design that aims to follow-up patients with residual disease after NACT or patients with metastatic breast cancer (mBC) to record the administered post-(neo)adjuvant respective palliative therapies and to collect information from routine longitudinal biomaterial samples (tissue and blood) to systematically assess tumor heterogeneity features over time by molecular profiling and biomarker analyses.

Hypothesis	The analysis of the residual tumor after NACT in eBC and of metastasis in mBC is relevant for identification of molecular mechanisms of treatment resistance and treatment sensitivity as well as to the identification of potential new treatment targets.
Study Objectives	
 
1. To assess tumor heterogeneity by analyzing longitudinal tumor samples.
 
2. To define biomarkers to predict resistance to systemic therapy, in the neoadjuvant, adjuvant and metastatic setting.
 
3. To describe the change in breast cancer subtype and in molecular markers after systemic therapy.
 
4. To identify new prognostic biomarkers associated with worse long-term outcome (e. g. disease-free, progression-free and overall survival).
 
5. To identify possible markers predictive for tumor sensitivity for post-neoadjuvant and palliative systemic therapies.
 
6. To identify new druggable targets which could be investigated for post-neoadjuvant and palliative treatment
 

Study Design	
MOMENTUM is a prospective registry trial with a non-interventional and translational design. The study will collect clinical data on patients with eBC and residual disease after NACT, and at the time of relapse as well as on patients with mBC. Longitudinal tumor tissue samples taken during routine assessments (diagnosis, surgery, etc.) will be collected to assess changes in tumor heterogeneity over time. Additionally, blood samples will be collected at the time of patient enrollment and later when oncologic treatment change due to progression is indicated to monitor molecular mechanisms of progression on ctDNA level (during routine visits).
 
The study aims to gain further insights into the genomic heterogeneity of breast cancer at critical timepoints of the disease and to analyze mechanisms of resistance to breast cancer treatment.

Inclusion Criteria	
 
1. Patients with eBC and clinically gross residual tumor after NACT or distant recurrence of breast cancer during/after (neo-)adjuvant therapy or mBC with progression after at least one line of therapy for mBC.
 
2. All patients must be able to provide a pair of longitudinal tissue samples namely: 
 
• one sample before NACT and one sample after NACT for patients with eBC
 
• one sample before and one sample after disease progression occurred for patients with mBC
 
 
 
3. Female and male breast cancer patients aged <math>\geq 18</math>.
 
4. Participation is allowed independently of breast cancer histology (ductal, lobular, others) and of breast cancer subtype (Luminal A, luminal B, HER2-
 

	
positive, triple-negative) but will focus on high-risk tumors such as TNBC and luminal B.
 
5. Informed consent for data collection and biomaterial collection.
 
6. Participation in other interventional clinical trials is allowed.

Exclusion Criteria	
 
1. Patients with a history of any malignancy beside breast cancer are ineligible with the following exceptions: 
 
a. Disease-free for at least 5 years (last assessment must have been performed within 3 months before inclusion) and the features of the primary tumor are considered low risk.
 
b. CIS of the cervix, basal cell and squamous cell carcinomas of the skin.
 
 
 
2. Patients with no histological verification of the diagnosis of breast cancer.
 
3. Patients with eBC or de novo mBC that have not received any systemic therapy.
 
4. Tissue acquirement either by biopsy or during surgery not possible.
 
5. Any physical or mental condition or severe comorbidities that would compromise the adequate cooperation of the patient.
 
6. History of significant neurological or psychiatric disorders that would prohibit the understanding of the study purpose and giving of informed consent.
 

Study Procedures and Examinations	
MOMENTUM is a non-interventional registry trial with a focus on real world patients. Clinical information on oncologic/medical history are collected at baseline, and follow up information on subsequent cancer therapies and oncologic outcome will be collected. To analyze association of molecular parameters with the clinical outcome, only tissues will be collected that were obtained during routine procedures (e. g. diagnostic core biopsy, surgery, etc.). The blood collection for whole blood and plasma sampling should be scheduled during routine visits. No study-specific interventional procedures or examinations are planned. The retrospective inclusion of deceased patients with secondary mBC and distant progression after initial neoadjuvant and/or adjuvant therapy and archived residual biomaterial and clinical data is possible in accordance with the "Empfehlung für die Bewertung forschungsbezogener Biobanken durch Ethik-Kommissionen empfohlen vom Arbeitskreis Medizinischer Ethik-Kommissionen Version 2.1. gemäß Beschluss vom 24.6.2022"

Patients	Approx.2000
FU	Patients will be followed-up for 5 years.
Sites	Ca. 50
Funding	The funding will be guaranteed by the GBG Forschungs GmbH.

## 7 Background

### 7.1 Introduction

Breast cancer in female patients has been the leading cause of global cancer incidence in 2020, with an estimated 2.3 million new cases, representing 11.7% of all cancer cases. Breast cancer is the fifth leading cause of cancer mortality worldwide, with 685,000 deaths. Five intrinsic breast cancer subtypes have been identified in the early 2000s based on different gene expression patterns and are currently used to select different targeted treatments.

In eBC, neoadjuvant chemotherapy (NACT) is a potential standard treatment option whenever chemotherapy is considered. A meta-analysis of nine randomized studies found that neoadjuvant and adjuvant therapy are equivalent in terms of survival and overall disease progression. However, the neoadjuvant approach allows for an *in vivo* sensitivity testing and permits to identify tumors, that are resistant to standard treatment. That way, patients who can potentially benefit from further therapy after surgery can be selected as well. Patients with a pathologic complete response (pCR) after NACT have a better prognosis than those without a pCR. The Food and Drug Administration (FDA) conducted a meta-analysis of 11,955 patients treated in twelve randomized NACT trials. Results showed that pCR in breast and axilla was significantly associated with improved event-free survival (EFS; ypT0 ypN0: HR 0.44; 95% confidence interval (CI) 0.39-0.51) and overall survival (OS; HR 0.36; 95% CI 0.30-0.44). This correlation was more pronounced in patients with aggressive breast cancer subtypes such as TNBC (HR [EFS] 0.24; HR [OS] 0.16) and in those with HER2-positive, HR-negative tumors who received trastuzumab (HR [EFS] 0.15; HR [OS] 0.08). The GBG meta-analysis conducted prior to the FDA analysis, demonstrated similar results. There was no correlation between pCR and EFS, but certain trials of the GBG such as the GeparSixto and GeparSepto trials demonstrated that an increase in the pCR rate can translate to an improved iDFS on a trial level.

Within the group of patients not achieving a pCR after NACT, prognosis can vary greatly, but is generally less favorable. A more precise information regarding prognosis is needed to facilitate decision making regarding adjuvant treatment strategies. A potential strategy to improve the outcome of patients without pCR after NACT, is the administration of additional therapy after surgery (post-neoadjuvant therapy). Despite the available treatment options, patients without pCR after NACT, especially having triple negative breast cancer (TNBC) or hormone receptor-positive BC with high CPS-EG score, still have a high risk of relapse but limited treatment options. The analysis of the residual tumor after NACT might help in understanding the mechanism of therapy resistance, identifying new markers of treatment sensitivity and new treatment targets allowing to better allocate patients in need for further treatment after NACT.

However, despite considerable advances in the treatment of eBC, treatment selection for patients, who did not achieve a pCR after NACT remains a clinical challenge. Available treatment agents from the metastatic setting (e.g., platinum salts, capecitabine, immune checkpoint inhibitors, cyclin-dependent kinase 4/6 inhibitors, PARP inhibitors, antibody-drug-conjugates) are emerging options as post-neoadjuvant strategies. Some of these medications are indicated in clearly defined situations, and even when selected properly, not effective for a great part of those patients. Based on these premises, selection criteria are critical to identify patients who may benefit from post-neoadjuvant

therapies, through the validation of prognostic and predictive biomarkers for a reliable risk assessment and estimation of benefit.

In the advanced breast cancer setting, patients usually receive multiple treatment lines, as consequence of tumor progression. However, each subsequent therapy is less effective in prolonging patients' progression free survival as drug resistances accumulate. Further investigations are of paramount importance to characterize breast cancer heterogeneity in therapy-resistant tumors and hopefully lead to a better understanding of resistance mechanisms and eventually to new target molecules.

## **7.2 Breast cancer heterogeneity and drug resistance**

Several mutations were identified to be likely drivers of disease progression. The International Cancer Genome Consortium (ICGC) examined the genomes of 100 breast cancer tumors and revealed their substantial heterogeneity. Putative driver mutations were discovered in several new cancer genes including *AKT2*, *ARID1B*, *CASP8*, *CDKN1B*, *MAP3K1*, *MAP3K13*, *NCOR1*, *SMARCD1* and *TBX3*. The Cancer Genome Atlas (TCGA) showed that high frequency somatic mutations were relatively few. In early breast tumors single nucleotide variations or genomic alterations (i.e. amplifications, deletions) in known breast cancer genes such as *PIK3CA*, *TP53*, *GATA3*, *MAP3K1*, *MLL3*, *CDH1* and *PTEN* were found. Additional mutated genes were identified, such as *CCND1*, *CCNE1*, *MDM2*, *CDKN2A*, *RB1* and *FBXW*. Furthermore, the role of the PI3K/AKT/mTOR, p53 and CCND1/CDK4/6/Rb signaling pathways activation was defined. All the analyses highlighted the heterogeneity of breast cancer, as assumed cause for the different treatment response and prognosis.

SATURN is a multidisciplinary consortium aiming to characterize intra-tumoral heterogeneity and its spatiotemporal evolution with single cell resolution longitudinally in patients using innovative tissue sampling schemes, then functionally explore the underlying mechanisms driving therapy resistance and metastasis, and eventually validate biomarkers and novel therapeutic strategies within clinical settings. Three high prevalent tumor entities will be analyzed, harboring common biological principles: Triple negative and luminal-B breast cancer, colorectal cancer, and pancreatic ductal adenocarcinoma. The data generated from these tumors will provide the basis for identifying generalizable rules and mechanisms of tumor evolution. To ensure identification of promising targets for clinical use, SATURN will take advantage of samples collected within the CATCH and COGNITION trials conducted under the responsibility of the university of Heidelberg. COGNITION is a prospective, non-interventional register and translational diagnostic study aiming to assess clinical features, genomics and molecular markers to identify patients with eBC for enrolment on marker driven trials. CATCH serves as companion program for COGNITION. While COGNITION focusses on eBC patients, CATCH focuses on mBC. Therefore, patients presenting initially eBC (enrollment in COGNITION) might be also enrolled into CATCH in case they present with metastatic disease throughout the course of the diseases.

MOMENTUM will collect samples that will be analyzed within SATURN. MOMENTUM is a prospective registry trial with a non-interventional and translational design aiming to follow-up patients with residual disease after NACT or metastatic disease to record the administered post-(neo)adjuvant and palliative therapies and collect the information from longitudinal routine biomaterial samples (tissue and blood) to systematically assess tumor heterogeneity features over time by molecular profiling and biomarker analyses. Additionally, mechanism of treatment resistance

will be analyzed. Therefore, patients are included in MOMENTUM at the time of disease-progression after neoadjuvant, adjuvant or metastatic therapy, and longitudinal samples before and after therapy are collected. Clinical information on oncologic/medical history are collected at baseline, and follow up information on subsequent cancer therapies and oncologic outcomes will be collected. To analyze association of molecular parameters with the clinical outcome, only tissues will be collected that were obtained during routine procedures. The new molecular approach might enhance the precision of treatment decisions. Optimal allocation to existing post-neoadjuvant/palliative treatment options on an individual basis is one possible achievement, discovery of innovative targets for post-neoadjuvant/palliative treatments and foremost identification of existing drug resistances thereby safeguarding patients from non-beneficial yet detrimental therapies would be most desirable.

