## 8 Study Objectives

1. To assess tumor heterogeneity by analyzing longitudinal tumor samples.
2. To define biomarkers to predict resistance to systemic therapy, in the neoadjuvant, adjuvant and metastatic setting.
3. To describe the change in breast cancer subtype and in molecular markers after systemic therapy.
4. To identify new prognostic biomarkers associated with worse long-term outcome (e. g. disease-free, progression-free survival and overall survival).
5. To identify possible markers predictive for tumor sensitivity for post-neoadjuvant and palliative systemic therapies.
6. To identify new druggable targets which could be investigated for post-neoadjuvant and palliative treatment.

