## 9 Study Design

MOMENTUM is a prospective registry trial with a non-interventional translational design. The goal of the trial is to obtain longitudinal biomaterial pairs (at least two tumor samples) representing different clinical situations, to assess molecular changes during disease progression. Eligible early breast cancer patients should preferably be enrolled in the study prior to surgery (after NACT) to allow for collection of fresh tumor tissue in addition to formalin-fixed paraffin embedded (FFPE) breast tumor tissue. Patients might also be enrolled after surgery to provide FFPE tumor tissue only. Patients with metastatic breast cancer may be enrolled only if they have received oncologic treatment and have experienced tumor progression during/after this therapy irrespective of the clinical situation in which therapy was applied (neoadjuvant/adjuvant or metastatic setting). Clinical information on oncologic/medical history are collected at baseline, and follow up information on subsequent cancer therapies and oncologic outcomes will be collected. To analyze association of molecular parameters with the clinical outcome, only tissues will be collected that were obtained during routine procedures. Archived samples from the primary tumor (untreated and/or after NACT) will be collected to assess molecular changes during tumor progression via longitudinal comparisons.

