## 10 Study Population

### 10.1 Inclusion Criteria

1. Patients with eBC and clinically gross residual tumor after NACT or distant recurrence of breast cancer during/after (neo-)adjuvant therapy or mBC with progression after at least one line of therapy for mBC.
2. All patients must be able to provide a pair of longitudinal tissue samples namely:
  - one breast tumor sample before NACT and one after NACT for patients with eBC
  - one sample before (breast tumor or metastasis) and one sample after (metastasis) disease progression occurred for patients with mBC.
3. Female and male breast cancer patients aged  $\geq 18$ .
4. Participation is allowed independently of breast cancer histology (ductal, lobular, others) and of breast cancer subtype (Luminal A, luminal B, HER2-positive, triple-negative).
5. Informed consent for data collection and biomaterial collection.
6. Participation in other interventional clinical trials is allowed.

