#### **14.6 Data Collection**

The following data will be collected:

- Baseline demographic and tumor characteristics
- Neoadjuvant Chemotherapy
- Surgery
- Post-neoadjuvant therapy
- Adjuvant therapy
- Clinical follow up on oncologic medications for treatment of metastasis and survival
- Biomaterial data (biopsies, blood samples)

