### **15 Follow up**

Data will be collected within the MOMENTUM study during recruitment phase. After LPI the data collection will be continued for all included patients for 5 years.

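### For the therapy that qualified a patient for enrolment, above all NACT, the registry has no unselected responders, so objective 2 cannot be estimated as resistant versus sensitive

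*Protocol*

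**What the plan says.** Objective 2 (Section 8) is "To define biomarkers to predict resistance to systemic therapy, in the neoadjuvant, adjuvant and metastatic setting". Objective 5, on sensitivity, is narrower: "To identify possible markers predictive for tumor sensitivity for post-neoadjuvant and palliative systemic therapies". It leaves neoadjuvant therapy out.

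Entry is set by inclusion criterion 1 in Section 10.1: "Patients with eBC and clinically gross residual tumor after NACT or distant recurrence of breast cancer during/after (neo-)adjuvant therapy", or metastatic disease that progressed after one or more lines. Section 9 adds that metastatic patients may enter only if they "have experienced tumor progression during/after this therapy irrespective of the clinical situation in which therapy was applied". Criterion 2 asks early breast cancer patients for a breast tumour sample from before NACT and another from after it. Section 7.2 summarises the selection in one sentence: "patients are included in MOMENTUM at the time of disease-progression after neoadjuvant, adjuvant or metastatic therapy".

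After entry, "follow up information on subsequent cancer therapies and oncologic outcomes will be collected" (Section 9), and Section 15 says "After LPI the data collection will be continued for all included patients for 5 years". Section 13 calls the work exploratory and descriptive and sets no statistical assumptions. The synopsis gives a target of about 2000 patients.

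**The concern.** A marker predicts resistance to a therapy if it is more frequent in tumours that resist the therapy than in tumours that respond. Estimating this needs both groups, sampled in a way that does not depend on the outcome. Here the outcome of the qualifying therapy is itself the entry condition. Marker frequencies among the enrolled describe resistant or incompletely responding tumours, and before/after pairs describe what changed under treatment. Neither shows that a marker present before treatment separates those who will respond from those who will not.

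The protocol does look towards such a use. Sections 7.2 and 11 (recruitment and consenting) both hope that resistance markers will spare patients ineffective treatment, which requires exactly this discrimination. If objective 2 stays as worded, a reader of later results could take frequencies in resistant tumours as evidence of prediction.

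**Working it through.** **1. Figure to reproduce.** There is none. The target of about 2000 is not derived, and Section 13 declines to set assumptions. The check is therefore a comparison of the entry routes with objective 2, followed by illustrations on stated assumptions.

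**2. Entry routes against objective 2** (Sections 9, 10.1 and 11.2)

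| Route | Qualifying therapy | Its outcome at entry | Unselected responders admitted? |
|---|---|---|---|
| Early disease | NACT | Gross residual tumour, with a post-NACT tumour sample required | No |
| Secondary metastatic, including deceased patients added retrospectively | Neoadjuvant and/or adjuvant therapy | Distant recurrence | No |
| De novo metastatic | One or more metastatic lines | Progression | No |

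No comparator from outside the registry is named for objective 2. COGNITION and CATCH appear in Section 7.2 as sources of samples for SATURN3, not as controls.

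**3. What entry on the outcome does to the contrast.** Let p1 be marker prevalence in enrolled (resistant) tumours and p0 the prevalence in sensitive tumours. Then OR = [p1/(1−p1)] / [p0/(1−p0)]. The registry observes p1 only.

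- Assume p1 = 0.20, so the odds are 0.25. A true OR of 1, 2 or 4 implies odds of 0.25, 0.125 or 0.0625 in the sensitive group, hence p0 = 20.0%, 11.1% or 5.9%.
- Assume p1 = 0.30, so the odds are 0.429. If p0 is 15%, 30% or 45%, the OR is 2.43, 1.00 or 0.52.

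The registry data are identical within each set, so even the direction of the association is unknown. A larger N makes p1 more precise and adds nothing about p0.

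**4. Relapsed patients with an earlier pCR.** Section 11.2 collects post-NACT surgical tissue from relapsed patients only where tumour remained, so patients with an earlier pCR can enter by relapsing. Section 7.1 gives an event-free survival hazard ratio of 0.44 for pCR against no pCR. Assume that this ratio applies to the qualifying relapse and that hazards are proportional. With non-pCR relapse risk r (assumed), the pCR relapse risk is 1 − (1−r)^0.44:

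- r = 20%: 9.4%, so 91% of pCR patients never qualify
- r = 30%: 14.5%, so 85% never qualify
- r = 40%: 20.1%, so 80% never qualify

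The minority who do enter are selected on relapse. Comparing them with relapsed non-pCR patients conditions on a later event that depends on NACT response and possibly on the marker. The comparison does not estimate the marker's association with response among all treated patients.

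**5. Therapies started after enrolment.** Here patients are followed forward and both outcomes can occur. As an illustration, assume marker prevalence 20%, hazard ratio 1.5 and two-sided 5%. Power is Φ(|ln 1.5|·√(d·0.2·0.8) − 1.96) for d events: 0.63 with 200 events, 0.90 with 400 and above 0.99 with 800. This contrast is estimable.

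**6. Graded outcomes of the qualifying therapy.** Amount of residual tumour and time to relapse or progression vary among those enrolled and can be related to markers. The comparison stays within patients who did not respond completely or who relapsed or progressed.

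**The case against.** The strongest reply is that a registry of therapy-resistant breast cancer enrols resistant disease on purpose, that Section 13 promises only exploratory description, and that contrasts belong in a statistical analysis plan that is not shown. The first two points lower the severity: no confirmatory test depends on this, and one part of one of six objectives is affected. They do not supply the missing group. Even a hypothesis about prediction needs variation in the outcome, and no analysis plan can recover patients who were not sampled.

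Other points on that side stand and limit the finding.

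- A reader might infer that objective 2 as a whole is unanswerable. The documents do not support that: later therapies and their outcomes are followed, as Sections 9 and 15 state.
- A reader might infer from "patients are included in MOMENTUM at the time of disease-progression after neoadjuvant, adjuvant or metastatic therapy" that therapy failed in every patient. That background sentence does not fit the early-disease route, which admits on residual tumour. Such patients may be partial responders.
- A reader might infer from Section 14.6, which lists "Clinical follow up on oncologic medications for treatment of metastasis and survival", that progression dates per line will not be recorded. That list names data domains, not case report form fields. Objective 4 names progression-free survival and Section 9 promises oncologic outcomes, so the omission cannot be inferred.
- No section says that frequencies will be reported as predictors. The risk lies in the wording of the objective.

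**Conclusion.** The point holds for the therapy that qualified the patient. Objective 2 cannot be estimated as resistant versus sensitive for NACT in the early-disease route, nor for the adjuvant or metastatic therapy that ended in the qualifying recurrence or progression. The neoadjuvant part is the clearest case, because NACT always comes before enrolment there and criterion 2 requires tumour after it. Relapsed patients with an earlier pCR do not repair this.

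The conclusion rests on the entry criteria and not on any assumed number. The prevalences, relapse risks, hazard ratio of 1.5 and event counts above are illustrations. Objective 2 remains answerable for therapies started after enrolment, and associations with graded outcomes remain possible within the selected group. This should be fixed, but it is not critical: it corrects the scope of a claim in an exploratory registry.

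**What to change.** Restate objective 2 in two parts.

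- (a) For therapy given before enrolment: describe alterations present in, or acquired by, resistant tumours, or their association with graded outcomes (amount of residual tumour, time to relapse or progression) within that selected group. Make no claim to predict resistance versus sensitivity.
- (b) For therapies started after enrolment: estimate predictive resistance markers, with relapse or progression versus none as outcome. Deceased patients included retrospectively have no such therapy and fall under (a) only.

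Remove the word neoadjuvant from the predictive claim unless the protocol names a source of NACT responders. Keeping patients with pCR in the registry for this purpose would conflict with criterion 2, and the documents show no archive of such samples, so neither is proposed here. Reconcile the Section 7.2 sentence on entry at progression with the residual-tumour criterion in Section 10.1, and carry the new objective into both synopses.

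The cost is wording only, with no new procedure or sample. The downside is a narrower objective.
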